## 2.3 RISK/BENEFIT ASSESSMENT

### 2.3.1 KNOWN POTENTIAL RISKS

The loss of information always exists, however provisions have been made to mitigate these risks. Participants may feel uncomfortable with the survey questions, or being in a group setting. We discuss this with participants at all times to measure their comfort and mitigate any concerns. Participants are also able to skip questions with which they are particularly uncomfortable.

### 2.3.2 KNOWN POTENTIAL BENEFITS

### 2.3.3 ASSESSMENT OF POTENTIAL RISKS AND BENEFITS

## 3 OBJECTIVES AND ENDPOINTS

OBJECTIVES	ENDPOINTS
Primary	
Use an iterative process between academic and community partners to adapt and modify the pilot TEEN HEED intervention	1) maintain/reduce body mass index (BMI)
Use qualitative methods to evaluate strategies for using peer educators and novel mobile health technologies as part of a group lifestyle change program for diabetes prevention among at-risk ethnic minority youth	2) improve adolescent dietary, physical activity and weight control behaviors, and
Use community-based participatory research strategies to refine, test, and evaluate outcomes of a peer education diabetes prevention program for pre-diabetic ethnic minority adolescents.	3) improve other measures of diabetes risk. We are collecting data at baseline and post intervention. We are also obtaining additional qualitative data and examining feasibility and acceptability for a text messaging program to support teens as they make lifestyle changes.

## 4 STUDY DESIGN

### 4.1 OVERALL DESIGN

We are now testing and evaluating outcomes of our refined intervention to reduce diabetes risk among ethnic minority pre-diabetic adolescents. We will further adapt the program for virtual delivery via a video conferencing platform to enhance access and attendance, and refine the text messaging platform to better support and engage teens.

We will identify at risk for diabetes adolescents and recruit adolescents (BMI in the overweight/obese range and HbA1c 5.7-6.4%) through electronic medical record data queries and referrals from clinical and community sites. Participation will be contingent on adolescent assent/parental consent (ages 13-17) or participant consent (ages 18 years or older). We will randomize pre-diabetic adolescents into intervention and wait list control (delayed intervention) groups to test intervention effectiveness. We will also evaluate the virtual and mHealth components of the intervention through usability testing and data analytics.

The intervention is 12 weekly 90-minute workshops based on feedback from our community advisory board and experts in peer led health education programs. The intervention will be offered via an online platform, Zoom, which is HIPAA compliant. We are testing the effectiveness of a virtual component versus our previous in-person workshop.

We are currently developing a technology-based component of the intervention based on findings from focus groups and with input from our Community Advisory Board (CAB). The technology-based tool is a secure mobile health platform we are developing in collaboration with a company called mPulse Mobile. The platform will allow us to securely send and track text messages, help participants set goals and monitor their behaviors, and provide participants with individualized feedback and positive reinforcement. Messages will be sent via an SMS text messaging mobile health platform to provide motivational messages regarding healthy eating, physical activity and healthy weight maintenance and to follow up on weekly goals made by the participants. The platform supports interactive dialogues including automated interactions using rule-based branching logic that allows participants to navigate through the program based on their message responses. In addition, natural language understanding allows real-time interpretation of text responses for more sophisticated dialogues. Beyond processing responses through automated dialogues, natural language understanding allows for responses that fall outside the scope of the dialogue's rules. mPulse Mobile's Engagement Console allows project staff to manage individual interactions with participants. The Console identifies any responses that cannot be handled by the messaging program's rules and flags these messages for staff to resolve. Additionally, staff can use the Console to manually initiate messages, and high-priority messages that must be reviewed can be escalated in real-time.

All information within the mPulse Mobile platform and cloud server is protected and secure. The platform ensures privacy and confidentiality of information shared and messages sent. The HITRUST Common Security Framework (CSF) is the most widely-accepted information technology security control audit framework developed explicitly for the protection of healthcare information. The framework integrates requirements from sources such as ISO, NIST, PCI, HIPAA, and others. To successfully complete the HITRUST CSF audit, mPulse Mobile had to

undergo a rigorous third-party vetting process consisting of baseline controls across many domains including information protection, endpoint protection, configuration management, disaster recovery, risk management, and physical security.

mPulse Mobile messaging programs follow compliance principles guided by Telephone Consumer Protection Act, Mobile Marketing Association's Consumer Best Practices, and CTIA Mobile Compliance Assurance Handbook. [name] will be the application manager.

All participants will also be advised about privacy issues surrounding responses to text messages. It will be recommended that they use a password to protect their cell phones. (Please see the previously submitted IT Security Risk Assessment Report).

We will be piloting the texting program with participants who had previously been enrolled in earlier version of the TEEN HEED study. We will obtain parental permission to allow mPulse Mobile to receive their cell phone numbers and send SMS text messages to participants. This information will be included in the study consent form with a separate place within the consent form for parents to initial to give this permission. Participants aged 18-19 will be asked to sign their own permission to receive SMS text messages from mPulse Mobile. We will make it very clear to participants that what is shared through the mobile dialogue is private, secure, and not shared with anyone beyond the program. We will also express that standard data and messaging rates from participant's provider may apply and that they can request that messages stop being sent at any time.

We will also conduct audio-recorded debriefing sessions with participants and peer leaders in which we will ask about their experiences with the intervention, reactions to the intervention, and ideas for intervention refinement. To monitor the community-academic partnership, we are tracking activities such as the communication between community-academic partners, number of participants at CAB meetings, number of manuscripts and presentations by academic-community partners, and policy-related outcomes. Additionally, we are investigating youth involvement in CBPR, through audio-recorded one-on-one interviews and qualitative analysis. This will help us understand how young people have helped shape the project. We are interviewing study participants, peer leaders, community action board members, interns, and study coordinators. They are being consented and asked questions about their personal experience with the study and their views on how young people have contributed to the project and how they may continue to do so in the future.

#### 4.2 SCIENTIFIC RATIONALE FOR STUDY DESIGN

Research suggests that like adults, young people are more likely to hear and personalize messages, and thus to change their attitudes and behaviors, if they believe the messenger is similar to them and faces the same concerns and pressures. However, relatively few studies have focused on peer led lifestyle interventions in youth.

#### 4.3 JUSTIFICATION FOR INTERVENTION

Rates of new diagnosed cases of type 2 diabetes are increasing among youth in the United States, with a disproportionate increase among minority youth. Lifestyle interventions leading to weight loss have

proven to be effective for diabetes prevention among overweight prediabetic adults, but few have been developed and tested in youth.

#### 4.4 END-OF-STUDY DEFINITION

A participant is considered to have completed the study if he or she has completed the baseline assessment and the follow-up assessment or has completed the text messaging program.

The end of the study is defined as completion of the 3-month follow-up assessment shown in the Schedule of Activities (SoA), **Section 1.3**.

## 5 STUDY POPULATION

## 5.1 INCLUSION CRITERIA

In order to be eligible to participate in this study, an individual must meet all of the following criteria:

## INCLUSION CRITERIA:

- Adolescents ages 13-19 years of age
- Residents of East or Central Harlem, members of an East or Central Harlem Institution, or patients seen in the Mount Sinai Health System. Membership in an East or Central Harlem institution includes the following: 1) attending a school in East or Central Harlem, 2) attending an after school or recreational activity in East or Central Harlem, or 3) receiving health care in East or Central Harlem. We will not ask participants for any identification for proof of address or membership in an East or Central Harlem institution. After informed consent is obtained for the adolescent to take part in the study, we will ask for the adolescent's full residential address. We will include those participants who live in supportive housing (such as shelters) and do not have plans to relocate from N.Y.C in the next year.
- Body mass index (BMI) percentile consistent with overweight/obesity (>85th percentile for age and gender based on Centers for Disease Control and Prevention definition).
- Hemoglobin A1c in prediabetes range (>5.7% or <6.5%)
- English speaking (resources available to us at this time limit inclusion of English speaking participants only). Note: only adolescents must be English speaking. Parental consent forms will be available in English and Spanish. The Spanish consent form will be submitted for IRB review with a letter of attestation from the translator after approval of the English consent form.
- Able to communicate verbally to participate in a group education class.
- Demographics:

(a) Gender: Males yes  no   
Females yes  no

(b) Age range: from 13 to 19  
(c) Racial and Ethnic Groups:

Caucasian	yes 	no 
Black	yes 	no 
Hispanic	yes 	no 
American Indian	yes 	no 
Alaskan Native	yes 	no 
Asian/Pacific Islander	yes 	no 
Other (specify) _____		

## 5.2 EXCLUSION CRITERIA

An individual who meets any of the following criteria will be excluded from participation in this study:

- <13 or >19 years of age
- Previous diagnosis of diabetes
- BMI percentile <85th percentile for age and gender based on Centers for Disease Control and Prevention definition
- Hemoglobin A1c outside of the prediabetes range (<5.7% or >6.4%)
- Currently pregnant
- Speaking a language other than English (resources to translate and implement all study activities in other languages are limited at this time)
- Cognitive or physical impairment that would preclude comprehension of a conversation and communicating as part of a group (i.e., dementia, deafness, inability to speak)
- On medications that may raise or lower blood sugar
- Plans to relocate from New York City within one year of enrollment
- Had, or is planning to have gastric bypass surgery
- Has a pacemaker or other implanted electronic device

## 5.3 LIFESTYLE CONSIDERATIONS

N/A

## 5.4 SCREEN FAILURES

Screen failures are defined as participants who consent to participate in this study but are not subsequently assigned to the study intervention or entered in the study. Individuals who do not meet the criteria for participation in this trial (screen failure) because of meeting one or more exclusion criteria that are likely to change over time may be rescreened. Examples include the successful treatment of a previous affective disorder, and the lifting of physical activity restrictions previously in place. Rescreened participants will be assigned the same participant number as for the initial screening.

## 5.5 STRATEGIES FOR RECRUITMENT AND RETENTION

The Principal Investigator [name], Research Coordinator [name] and community partners working on this study previously identified venues for recruitment of adolescents in East

and Central Harlem including youth community based organizations, after school programs, and health care centers.

Recruitment sites may include the following community organizations in East Harlem with whom we have previously collaborated: Union Settlement Association, Harlem RBI, East Harlem Boys Club, Children's Aid Society, Stanley Isaacs Neighborhood Center, SCAN(SUPPORTIVE CHILDREN'S ADVOCACY NETWORK), Harlem Children's Zone, and other interested organizations to be identified by our community partners and project board. Possible clinical sites for recruitment include Mount Sinai's Adolescent Health Center, Mount Sinai's pediatric endocrine clinic, Mount Sinai's Pediatrics Associates practice, Settlement Health, Boriken Neighborhood Health Center, the Institute for Family Health, Mount Sinai School Based Health Clinics, and Mount Sinai Pediatric Emergency Rooms.

We will obtain provider referrals from community based clinics. We will use Mount Sinai's Data Warehouse and/or EPICs slicer/dicer to identify potentially eligible subjects for recruitment from the Mount Sinai General Pediatric Faculty Practice, Pediatric Endocrinology and Diabetes Center, and the School Based Health Clinics. We will request the following fields:

Name, medical record number, date of birth/age, address, gender, parent or guardian name, contact information for teens 18-19 (including telephone number or other numbers provided), parent or guardian contact information for teens ages 13-17 (including telephone number or other numbers provided), BMI (BMI percentile when available), medications prescribed, and laboratory values from the past year: Glucose/preserved glucose, hemoglobin A1c (values), total insulin (values), and lipid panels (values). We will request information for eligible patients whose medical records contain the following diagnoses codes: overweight, obesity, prediabetes, insulin resistance, and acquired acanthosis nigricans.

We will obtain only the minimum amount of PHI necessary to contact potentially eligible teenagers. We will meet with providers and ask them to consent to contacting their patients who they think may be eligible. Contact information will be immediately deleted from the server for those who are not interested in participating or who are not eligible for the study. Participants will be given the opportunity to decline being re-contacted should they not be interested in participating.

For Collaborating Community sites – As described above, site leaders will verbally inform potential subjects about TEEN HEED and provide interested children with a letter for parents. For adolescents ages 18 or 19 years who meet eligibility requirements and are interested in the study, we will obtain informed consent prior to participation in the study. For adolescents ages 13-17 years, who meet eligibility requirements and are interested in the study, we will obtain assent of the adolescent and obtain consent from his/her parent or guardian. The combined Parental Consent and HIPAA Authorization Form will be obtained in person or over the phone by a member of the study staff. After consent is obtained, we will invite adolescents for their official baseline visit. Eligible adolescents will be randomized into intervention and wait list control groups. Intervention participants will attend a 12-week peer led workshop and follow up assessments.

We will recruit potential peer leaders through our contacts at community youth organizations in East and Central Harlem and local schools. Peer leaders will attend training sessions, workshop

sessions and debriefing sessions. All classes will be led by trained adolescent peer leaders. Qualifications to be a peer leader are: 1) older than 18 years of age 2) fluency in English and 3) ability to communicate well in a group setting. Peer leader training will include information about not divulging information (e.g., conditions, treatments, personal background or any other confidential or non-public information) concerning participants attending the classes. We will also have the leaders sign a Statement of Confidentiality. Peer leaders will be paid \$100 to attend the training session and \$300 for leading each 12 week workshop

Participants will be given a \$40 gift card at each study visit as compensation for their time.

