**Study Description:**

Specific Aims: 1) Explore strategies for using peer educators and novel mobile health technologies as part of a group lifestyle change program for diabetes prevention among at-risk ethnic minority youth in a New York City community with high disease burden. 2) Refine, implement, and evaluate outcomes for the intervention. Using preliminary data, we will use CBPR to refine our developmentally and culturally appropriate lifestyle intervention for pre-diabetic ethnic minority adolescents. We will then screen at-risk adolescents for pre-diabetes and related lifestyle and biological measures and compare outcomes in adolescents in intervention and wait list control groups to test intervention effectiveness. 3) Further refine the intervention for a larger RCT based on an examination of intervention feasibility, acceptability, and sustainability.

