**Phase\* or Stage:**

**Description of Sites/Facilities Enrolling Participants:**

*All programming will be offered via Zoom. In-person study visits for baseline, 5m, and 12m, will be conducted at our pediatric clinic.*

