**1.2 SCHEMA**

**Flow Diagram (e.g., randomized controlled trial)**

**1.3 SCHEDULE OF ACTIVITIES (VIRTUAL TEEN HEED)**

	Pre-screening (Pre-consent)	Visit 1 Baseline	12-week workshop	3m visit
EMR Review Eligibility	X			
Informed Consent		X		
Demographics		X		
Clinical history		X		
Height & Weight		X		X
Outcome Evaluation				
Workshop assessments/Action Planning			X	
Health and Lifestyle Questionnaire		X		X
Debrief session			X	
Adverse Events Reporting		X	X	X

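### The wait-list group is not defined as a comparator: the available text gives it no assessment time and no crossover point, the follow-up visit times conflict, and Section 6.3 denies the randomisation that would create it

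*Combined protocol and SAP*

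**What the plan says.** **Comparison and allocation.**
- The synopsis (Section 1.1, Study Description) will "compare outcomes in adolescents in intervention and wait list control groups to test intervention effectiveness".
- Section 4.1: "We will randomize pre-diabetic adolescents into intervention and wait list control (delayed intervention) groups to test intervention effectiveness".
- Section 5.5: "Eligible adolescents will be randomized into intervention and wait list control groups". The next sentence is "Intervention participants will attend a 12-week peer led workshop and follow up assessments". No matching sentence follows for the wait-list group.
- Section 6.3 says the opposite about allocation: this pilot does not randomise.

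**Visits.**
- The Section 1.3 table has four columns, in this order: pre-screening, baseline, 12-week workshop, 3m visit. No column is labelled by group and none is for a delayed workshop. Height and weight are taken at baseline and at 3m.
- Section 4.4: "The end of the study is defined as completion of the 3-month follow-up assessment".
- The synopsis instead has "In-person study visits for baseline, 5m, and 12m, will be conducted at our pediatric clinic", with a participant duration of 12 months.

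**Wait-list procedures.** The only procedure written specifically for the wait-list group is in Section 6.1.1, where they too are asked to agree to their phone numbers going to the texting vendor.

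**Analysis.** Sections 8.1, 9.1 and 9.4.1 test change from baseline to follow-up. Section 9.4.1 mentions confidence intervals for intervention parameters but does not write out a between-group contrast. Section 9.4.2, on the primary endpoint, is a heading without text.

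**The concern.** A wait-list group works as a control only if its endpoint is measured while it is still waiting, at a time that matches the treated group. The plan needs three things for this: a control visit, a time origin shared by both groups, and a start for the delayed workshop that falls after that visit. None is in the available text.

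Staff who follow the document as written could leave controls unmeasured, or take them through the single track and measure them after the workshop. Neither can be repaired later, because an untreated measurement cannot be taken once the participant has crossed over. The effectiveness comparison in the synopsis and Section 4.1 would then be lost or mistimed. Unequal elapsed time matters most for raw BMI (Sections 3 and 9.4.1), which changes as adolescents grow. It matters less for BMI percentile (synopsis, Sections 8.1 and 9.1), which is already referenced to age.

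**Working it through.** The plan states no figure on this point, so there is none to reproduce. The check is a side-by-side reading and some timing arithmetic.

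**1. Can the 1.3 track be applied to controls as it stands?** It runs baseline, workshop, 3m visit. There are three ways to read it:
- *It covers intervention participants, as the sentence in Section 5.5 suggests.* Controls then have no scheduled follow-up.
- *It covers everyone, column by column.* Controls are then measured after the workshop, so the contrast is treated versus treated.
- *It covers everyone, but controls skip the workshop column, attend 3m and cross over afterwards.* This gives a valid contrast, but the rule is not in the text.

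**2. Which visits are unexposed for controls?** Suppose the visits apply to everyone and count both schedules' times (3, 5 and 12 months). The workshop lasts 12 × 7 = 84 days; 84 / 30.4 ≈ 2.8 months. The crossover time is not stated, so the rows below are assumptions.

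| Assumed start of delayed workshop | Ends about | 3m | 5m | 12m | Unexposed visits |
|---|---|---|---|---|---|
| just after 3m | 3 + 2.8 = 5.8 months | before | during | after | 1 |
| just after 5m | 5 + 2.8 = 7.8 months | before | before | after | 2 |
| just after 12m | beyond the 12-month participation | before | before | before | 3 |

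A delayed workshop completed before the 12-month visit makes that visit a treated-versus-treated comparison.

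**3. When is the 3m visit?** Its origin is not given. Twelve weekly sessions span 11 × 7 = 77 days from first to last, and 3 months is about 91 days. Let w be the days from baseline to the first session. The last session is on day w + 77, so a visit counted from baseline precedes it whenever w > 91 − 77 = 14 days.

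The documents do not give w. For illustration, assume w is 2 to 8 weeks (14 to 56 days):
- The last session falls on day 14 + 77 = 91 to day 56 + 77 = 133.
- A visit on day 91 then falls 0 to 42 days (0 to 6 weeks) before the last session.
- If intervention participants are instead seen at their last session and controls on day 91, the groups differ by the same 0 to 42 days of elapsed time.

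The table order and the post-intervention wording of Sections 8.1 and 9.1 favour a visit after the workshop. A visit tied to the workshop's end has no counterpart in controls until the plan defines one, for example through the cohort they were randomised with.

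**The case against.** A reader might infer that follow-up is restricted to the intervention group, that no control will have a follow-up BMI, and that the wait-list group therefore cannot serve as a comparator. The documents do not support that.

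- **Silence is not exclusion.** Section 5.5 concerns recruitment and does not bar controls from follow-up. The visits in the synopsis and Section 1.3, the loss-to-follow-up rule in Section 7.3 and the gift card in Section 5.5 are not specific to a group. Nor is Section 4.4: "A participant is considered to have completed the study if he or she has completed the baseline assessment and the follow-up assessment", with the texting programme as an alternative route. A plan to compare outcomes between groups also presupposes control outcomes.
- **The Section 1.2 flow diagram is not reproduced in the text available here.** It may show a wait-list path or a crossover point.
- **Ending the study at 3 months is not itself a contradiction.** The delayed workshop may follow the last assessment, which would keep controls unexposed.
- **The 5- and 12-month visits match the follow-up of the earlier cohort in Section 2.2.** They may be carried over, in which case the 12-month contrast does not arise.
- **Section 6.3, the single track and the baseline-to-follow-up tests all fit a one-arm pilot.** The first question would then be whether a control group exists.

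All five points stand, and they limit the finding to a lack of definition. They do not remove it. The reading that rescues the comparison needs a rule that staff would have to supply, and the text also supports readings under which the comparison fails.

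**Conclusion.** The concern holds as a failure to define the comparator. In the available text the wait-list group has no stated assessment time, visit origin or crossover point; the follow-up times conflict (3 months against 5 and 12 months); and the plan contradicts itself on randomisation. Of the three readings of the Section 1.3 track, two give no usable control measurement, and the third depends on an unwritten rule. Under generic visits, one to three of the named follow-up times are unexposed, depending on the assumed crossover.

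The 0-to-6-week timing gap rests on an assumed wait of 2 to 8 weeks and is an illustration only. The growth argument applies to raw BMI more than to BMI percentile. The conclusion also depends on the missing Section 1.2 diagram not settling the matter. It should be corrected before enrolment, because a missed pre-crossover measurement cannot be recovered.

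**What to change.** First reconcile the synopsis and Sections 4.1 and 5.5 with Section 6.3 on whether there is a randomised control group. Then reconcile the synopsis visits and 12-month duration with Sections 1.3 and 4.4.

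If the wait-list comparison is kept:
1. Add a wait-list track to Section 1.3 with the same height and weight, questionnaire and adverse-event rows. Amend Section 5.5 so that both groups attend follow-up. Make the Section 1.2 diagram agree.
2. State the origin of the follow-up visit. Measure controls at the same elapsed time from randomisation as the intervention participants randomised with them, for example by calling both when that cohort's workshop ends. Take this measurement before the control's delayed workshop begins.
3. State in Section 9.4 that the primary contrast is between groups at that visit, and that visits after crossover do not enter it.

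If the study is single-arm, remove the wait-list comparison and the effectiveness claim that rests on it.

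The cost is an amendment and one brief visit per control at the clinic already in use, with the $40 card that Section 5.5 already promises at each visit. The one constraint on conduct is that a control's delayed workshop cannot start before that visit.
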